2.4 Analyses

The primary outcomes include opioid use and DSM-5 diagnosis of opioid use disorder via modified CIDI-2 Substance Abuse Module at 6-months post-intervention. Opioid use will be computed from the Timeline Follow-Back (TLFB) as the number of days of self-reported opioid use in the past 30 days at the 6-month assessment. The cost analysis will measure and value resources associated with VI, including medical personnel (physician/nurses), labs, and medications. To ascertain cost-effectiveness ratios of VI and PNV, cost data will be compared to changes in key clinical measures of effectiveness.

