5.4 Participant Recruitment

Recruitment through a close collaboration with the Bernalillo County Metropolitan Detention Center (BCMDC) staff, combined with IRB-approved presentations and posted announcements in the jail facilities will proceed until 150 participants are recruited, consented, and randomized. Given the potential recruitment pool of more than 80 individuals per month, it is expected that an average of 6-8 individuals will be randomized per month across the 20-month enrollment period. Based on prior evidence in similar trials, refusals and early (pre-randomization) dropouts will account for approximately 20% of individuals presenting for screening.

Recruitment plans include hypervigilence to the issue of voluntariness. All BCMDC and study staff will be extensively trained on this issue to ensure that their actions and words do not convey any level of coercion. Training will include a discussion of the fact that treatment and study compliance are optimized when participants have the opportunity to consider the study, ask questions, and provide voluntary consent to participate. Furthermore, all recruitment documents and the ICF will emphasize that decisions whether or not to participate are solely up to the individuals, that the decision will not affect the treatment or possible treatment to which the individual is eligible, that participation/non-participation will not affect the sentence, release, probation, or any other aspect of the individual's incarceration.

The main method of recruitment will be announcements of the study made to inmates in the Bernalillo County Metropolitan Detention Center (BCMDC). An informational flyer will be provided to arrestees who are within 4 weeks of release and have been detoxified from opioid use. Individuals who convey interest in this study to jail staff will be referred to study staff. If still interested after receiving a description of this study, study candidates will complete a consent process that includes an detailed explanation of the study, risks and benefits, and that study

participation is voluntary and will have no effect on a participant's sentence, jail term, probation, parole, or release.

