6.1 Primary Outcome Measure

The primary outcomes will be opioid use and a DSM-5 diagnosis of opioid use disorder 6 months after randomization.

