8.2 Drug Use Measures and Psychological Measures

8.2.1 Substance Use Report: Timeline Follow-Back (TLFB)

The TLFB will be used to elicit participants' self-reported use of alcohol and illicit substances. At screening, substance use reported by the participant for the prior 30-day period will be assessed. The TLFB will be administered at each study visit throughout the medication phase, at the post-medication visit, and at follow-up to document the participant's self-reported use of substances for each day since the previous assessment.

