10.0 STATISTICAL ANALYSES

The project emphasizes evaluation of the clinical utility of Vivitrol in jail inmates as compared with a Drug Education condition (DE), while descriptive statistics will provide an overall assessment of the implementation of the protocol.

Analyses will include an Intent-to-treat (ITT) design such that all randomized participants who received at least one dose of medication (VI, PNV), or received at least one session of drug education (DE) will be included who did not violate the protocol in a way that could potentially affect the efficacy results. Participants will be excluded from the Protocol Population (PP) if:

- 1. concomitant medication that is known to have significant clinical effect on primary or secondary endpoints was administered.
- 2. Violations of the inclusion or exclusion criteria are judged to affect the efficacy evaluations.

Subjects in the PP population will be allocated to treatment groups in the analysis based on the actual treatment they received. If there is substantial difference between the ITT population and the PP population, all analyses described below will be performed using only subjects in this group.

All statistical tests will be performed using two-sided .05 significance levels, unless otherwise stated. All comparisons between treatments will be reported with parameter estimates and 95% confidence intervals. For parameters measured at baseline and subsequently, the variables of interest are changes from baseline.

Post-baseline variables will not be imputed; estimates can be obtained using the hierarchical models specified below under the assumption of missing at random. For the primary outcome measure, diagnosis at six months, subjects who have dropped out for whatever reason will be considered to retain the diagnosis. Other outcome measures for which data are missing will be imputed using multiple imputation methods. Sensitivity analyses will repeat specific analyses using permutation tests of at least 1000 samples.

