10.4 Analysis Approach

Analyses will employ modeling approaches that are less sensitive to biases from missing data, using a technique that conceptualizes missing data in two ways: intermittent missing data for participants active in the trial and dropouts (Shoptaw et al., 2002). Analysis of urine drug screen results are conducted using aggregates such as the Treatment Effectiveness Score (Ling et al., 1997), which is tested by condition using GLM and non-parametric strategies, where appropriate. Retention differences between conditions will be tested using an appropriate survival analysis model. Counts and composites of scores on drug craving and psychological measures will also be analyzed by treatment condition using t-tests and ANOVAs. Secondary analyses may include use of longitudinal models (Diggle et al., 1994), including normal mixed-effects models (Littell et al., 1996; SAS Institute, 1996; Singer, 1998; MIXED; PROC MIXED, SAS Institute Inc, Cary, NC) for continuous measures and generalized linear mixed models (Littell et al., 1996; GLMM; GLIMMIX macro, SAS Institute, Inc) for categorical measures. A six-step analysis approach is described below.

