10.4.2 Primary Statistical Analysis of the First Primary Outcome Measure

A mixed effects logistic regression will used to model the binary primary outcome measure; the diagnosis of opioid use disorder at six months post treatment. are modeled as a linear combination of predictor variables. A logit link function will be used to link subject covariates to the probability of success There will be two levels in the model: within sites and between sites. The model will included treatment, cluster (site) and baseline covariates as fixed effects and subject as a random effect. Indicator variables will identify whether a subject has received XR-NTX, methadone and a behavioral intervention (PN.) Site by treatment interactions will be included in the model. Interactions that are statistically significant at the 10% level will be investigated and may imply that analyses of individual sites is required. In this case, relevant contrasts will be performed within the sites.

Additional covariates will include age, gender, whether a subject had prior methadone maintenance treatment and baseline self-reported cocaine use. Other possibilities mediating

factors include opioid dependence severity at baseline, concurrent cocaine or alcohol and/or benzodiazepine misuse, and homelessness.

SAS PROC Mixed will be used to perform the analysis. The coefficients in the model will be estimated by generalized least squares (GLS), with covariance parameters estimated by restricted maximum likelihood (REML). Standard errors of the parameter estimates will be computed using the model. This procedure assumes that missing observations are ignorably missing or missing at random (MAR).

The primary contrast is a comparison of the probability of a DSM-5 Opioid Use Disorder Diagnosis at 6 months for those on medication versus those receiving enhanced treatment as usual (etau.) The contrast will utilize XR NTX data from both the NYU and UCLA and Interim Methadone data from FRI; the medication plus PN treatment arm will not be included.

Descriptive statistics will examine feasibility issues of the pharmacotherapy, analyzing AEs, side effects, and patient and clinician acceptance, and reasons for early termination or post-randomization refusal of assigned condition. Single-point, between-group comparisons of these measures can be tested using t-tests or ANOVAs for continuous variables and chi-square for binary measures.

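### Section 10.0 directs change from baseline where section 2.4 defines opioid use as a month-6 level, and nothing commits the plan to adjusting opioid-use days for their screening value

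*Combined protocol and SAP*

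**What the plan says.** Section 6.1 names two primary outcomes: "The primary outcomes will be opioid use and a DSM-5 diagnosis of opioid use disorder 6 months after randomization".

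On the variable to be analysed, two places disagree.
- Section 2.4 (Analyses) computes opioid use from the Timeline Follow-Back (TLFB) as the "number of days of self-reported opioid use in the past 30 days at the 6-month assessment". This is a level.
- Section 10.0 gives a general rule with no exception: "For parameters measured at baseline and subsequently, the variables of interest are changes from baseline". Opioid use is such a parameter, since section 8.2.1 says: "At screening, substance use reported by the participant for the prior 30-day period will be assessed".

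On the model, section 10.4.2 is headed "Primary Statistical Analysis of the First Primary Outcome Measure" and covers the diagnosis: "A mixed effects logistic regression will used to model the binary primary outcome measure". No matching section follows for opioid use.

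What remains is generic. Section 10.4 says that counts and composites of scores on craving and psychological measures "will also be analyzed by treatment condition using t-tests and ANOVAs", and allows mixed models as optional secondary analyses. Section 10.2 lists TLFB days among the secondary outcomes, under descriptive, binomial and multinomial methods. Section 10.4.1 brings in baseline variables as covariates only where the arms are found to differ. The covariates in section 10.4.2 belong to the diagnosis model and do not include screening opioid-use days.

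**The concern.** One of two primary outcomes has two conflicting analysis variables and no named model. In an open-label trial (section 7.14) that leaves the choice open until outcomes can be seen.

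The conflict also bears on efficiency. If the section 10.0 rule is followed literally and the change is compared between arms without a baseline term, the screening value is subtracted with a fixed weight of 1 instead of the weight that the data support. When screening use predicts month-6 use only weakly, the subtraction adds noise. With about 120 evaluable participants in three arms, that loss is worth avoiding, and the screening values are already collected. Craving (VAS) is in the same position: it is measured at screening and afterwards, and section 10.4 sends it to t-tests and ANOVAs.

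**Working it through.** **Inputs from the documents.** 150 randomised 1:1:1, about 120 evaluable, so 40 per arm (section 10.3); two-sided 0.05 (section 10.0); effect size d = 0.5 (section 10.3).

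**Inputs assumed.** The correlation between screening and month-6 values, ρ, from 0 to 0.9; the ratio of baseline SD to month-6 SD, k, from 0.25 to 1.25. Neither is in the documents. The outcome is treated as normal with month-6 SD 1. The comparison is a two-sample t of 40 v 40, computed with the noncentral t; the baseline slope is treated as known.

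**The plan's own figures.** Section 10.3 gives power of about 0.70 for d of about 0.60 and 0.80 for d = 0.5. At 40 v 40 the t-test gives 0.755 and 0.598. The stated figures are not reproduced. That is a separate matter; 0.60 is the reference value below for a plain month-6 comparison at d = 0.5.

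**Variances, in units of month-6 variance.**
- Month-6 level: 1
- Baseline-adjusted month-6 value: 1 − ρ²
- Unadjusted change: 1 + k² − 2ρk = (1 − ρ²) + (k − ρ)²

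The last identity settles the ordering. The change score carries an extra (k − ρ)², which is never negative and is zero only when k = ρ. Change is noisier than the plain level when ρ < k/2, which at k = 1 means ρ < 0.5.

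**Equal SDs (k = 1).** The change variance is 2(1 − ρ), and its ratio to the adjusted variance is 2/(1 + ρ).

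| ρ | Variance: change | Variance: adjusted | Ratio | Power: change | Power: level | Power: adjusted |
|---|---|---|---|---|---|---|
| 0 | 2.00 | 1.00 | 2.00 | 0.35 | 0.60 | 0.60 |
| 0.3 | 1.40 | 0.91 | 1.54 | 0.46 | 0.60 | 0.64 |
| 0.5 | 1.00 | 0.75 | 1.33 | 0.60 | 0.60 | 0.72 |
| 0.7 | 0.60 | 0.51 | 1.18 | 0.81 | 0.60 | 0.87 |
| 0.9 | 0.20 | 0.19 | 1.05 | 0.999 | 0.60 | 0.999 |

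The normal formula gives values about 0.01 higher over most of the table and the same pattern.

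**Unequal SDs, ρ = 0.3 (adjusted power 0.64 throughout).**
- k = 0.25: change variance 0.9125, power 0.64; practically no loss.
- k = 0.3: change variance 0.91, equal to the adjusted variance; no loss.
- k = 0.5: change variance 0.95, power 0.62. Here change does better than the plain level (0.60).
- k = 1.25: change variance 1.8125, power 0.37; a larger loss than at equal SDs.

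**Which k is plausible.** The flyer goes to "arrestees who are within 4 weeks of release and have been detoxified from opioid use", so the 30-day screening window can overlap custody, whereas month 6 follows release. That could lower ρ or compress the baseline spread. A smaller k reduces the loss only if it brings k nearer to ρ. At ρ = 0.7, moving from k = 1 to k = 0.25 takes change power from 0.81 to 0.74, against 0.87 adjusted.

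**The case against.** The strongest reply is that the plan never commits to the inefficient analysis. Section 2.4 is specific to this outcome and fixes the month-6 level, while the section 10.0 sentence is general. In a linear model, change analysed with baseline as a covariate gives the same treatment effect and precision as the adjusted month-6 value. So a missing model is a gap in pre-specification and does not in itself cost power. This stands: a reader might infer a chosen change-score analysis and a certain loss, and the documents do not support that.

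Three further inferences are tempting and should be avoided.
- That opioid-use days are assigned to t-tests and ANOVAs. The section 10.4 sentence concerns craving and psychological measures and does not clearly reach TLFB days; section 10.2 lists those days under other methods.
- That HIV-risk scores are affected in the same way. Section 10.2 gives the HIV-GAIN repeated-measures procedures, and whether these behave like change scores depends on a parameterisation that is not stated.
- That change is worse than the level whenever ρ is below 0.5, or always worse than adjustment. The first needs equal SDs; the second fails at k = ρ, where they tie.

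It is also fair that section 10.3 describes a study focused on feasibility and not powered for exhaustive comparison, and that normal formulas only approximate a bounded 0–30 count. The 40 v 40 powers do not describe the section 10.4.2 contrast, which sets medication against enhanced treatment as usual using data from several sites.

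What survives is that sections 10.0 and 2.4 cannot both govern the same outcome, and that no text secures the baseline adjustment.

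**Conclusion.** The point holds as an unreconciled conflict over the analysis variable, with no model for the opioid-use primary outcome and no planned adjustment for its screening value. Choosing the adjusted month-6 analysis is an efficiency gain and a matter of pre-specification; a change score would not be invalid.

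The size is conditional on change being analysed without a baseline term. At d = 0.5, 40 per arm and equal SDs, the power lost runs from about 25 points at ρ = 0, through 18 at 0.3, 12 at 0.5 and 6 at 0.7, to practically none at 0.9. With unequal SDs it can be larger or smaller, and it is nil when the SD ratio equals ρ. The direction is secure apart from the small cost of estimating the baseline slope; the size rests on ρ and k, which the documents do not give, and on a normal approximation to a bounded count.

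**What to change.** 1. Replace the change-from-baseline sentence in section 10.0 so that it agrees with section 2.4: the month-6 value is the analysis variable, and change scores are reported descriptively.
2. Analyse the month-6 value with treatment, the screening value and the two urn factors (opioid type and gender, section 7.3) in the model, whether or not the arms differ at baseline.
3. For opioid-use days, add a section parallel to 10.4.2 that pre-specifies one model suited to an overdispersed count out of 30 and states its treatment contrast explicitly. Neither should be borrowed by reference: section 10.4 names the generalised linear mixed model only for categorical measures as an optional secondary analysis, and the section 10.4.2 contrast is medication against enhanced treatment as usual across sites.
4. Apply the same baseline adjustment to VAS craving.

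The cost is SAP wording and slightly more analysis work. No new data are needed, because the screening values are already collected.

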10.4.1 Data Screening

Typical data screening activities will be conducted; univariate analyses will determine cell frequencies, normality, linearity, and homoscedasticity of continuous variables, and missing values. Variables with non-normal distributions will be transformed, when appropriate, using procedures recommended by Mosteller and Tukey (1977). Missing values will be handled using conventional case elimination, mean substitution, or estimation procedures (e.g. Cohen & Cohen, 1983). Preliminary analyses will address baseline characteristics of the two medication conditions using univariate techniques to determine the adequacy of the random assignment procedures, and whether these procedures result in groups similar in pertinent characteristics. Any variables determined to differ significantly between conditions will be used as covariates. We will also conduct attrition analyses to determine whether participants who failed post-consent screening differ from those randomized.

Baseline Characteristics and Treatment Group Differences

To appraise differences in baseline characteristics of the treatment groups, continuous variables will utilize analysis of variance, ordinal variables will utilize the Cochran Mantel Haenszel test, and dichotomous variables will utilize the chi-square (χ^2) test or Barnard's test. As appropriate, transformation such as log, square root or inverse may be utilized to accomplish the twin goals of variance stabilization across levels of the predictor variables and normal distribution of the outcome variable, if necessary.

For continuous variables, the number of non-missing and missing values and the median, mean, standard deviation, minimum, and maximum will be obtained for each treatment group. For categorical variables, the counts and proportions of each value will be tabulated.

Differences between participants who were considered but not randomized (screen fails) will be compared with randomized participants on selected demographic characteristics. Summary tables for continuous variables include mean, standard deviation, median, min and max will be prepared. Outcome measures will be summarized by treatment group and by visit when applicable.

Treatment group differences at the 0.10 level of significance in baseline variables may be included as stratification variables or covariates in efficacy analyses.

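### Section 10.0 gives two incompatible missing-data rules for the non-diagnosis outcomes, including six-month opioid days; other sections add more, none is ranked, and no sensitivity analysis varies the missing-data assumption

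*Combined protocol and SAP*

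**What the plan says.** Section 10.0 contains three statements in sequence:

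- After baseline, as a general rule: "Post-baseline variables will not be imputed; estimates can be obtained using the hierarchical models specified below under the assumption of missing at random".
- Six-month diagnosis: "subjects who have dropped out for whatever reason will be considered to retain the diagnosis".
- For the rest: "Other outcome measures for which data are missing will be imputed using multiple imputation methods".

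Other sections add to these:

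- **7.3** counts anyone who ends participation after induction or the first drug education session as a treatment failure, under an intent-to-treat heading.
- **10.4** commits to a technique that treats intermittent gaps and dropout separately.
- **10.4.1**, under data screening, says "Missing values will be handled using conventional case elimination, mean substitution, or estimation procedures".
- **10.4.2**, headed "Primary Statistical Analysis of the First Primary Outcome Measure", gives a mixed logistic model for the diagnosis and says that it assumes data missing at random (MAR). No section covers a second primary outcome.

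On robustness, 10.0 says "Sensitivity analyses will repeat specific analyses using permutation tests of at least 1000 samples". Sections 10.4 and 10.4.2 also plan a survival analysis of retention and a description of "reasons for early termination or post-randomization refusal of assigned condition".

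Sections 6.1 and 10.1 list opioid use with the diagnosis as primary outcomes. Section 2.4 (Analyses) defines opioid use as TLFB days out of the last 30 at the six-month assessment. The same measure also appears among the secondary outcomes in 4.3.2, 6.2 and 10.2.

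**The concern.** An outcome cannot be both left unimputed and multiply imputed in its main analysis. For TLFB opioid days the plan does not settle which rule produces the reported result. The first rule depends on hierarchical models described later in the plan, but the only one definitely specified is for the diagnosis. Without a model for TLFB days, leaving them unimputed could in practice mean a test on whoever was observed at month 6.

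The trial is open-label (7.14), and 10.3 expects less dropout with Vivitrol alone (VI) than with drug education (DE). A missing-data method chosen after outcomes are known would be hard to defend. Permutation changes the reference distribution of a test. It does not show how the estimate depends on what is assumed about absent participants.

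**Working it through.** **Scope of the two rules.** The diagnosis has its own sentence between them, so the outcomes covered by the multiple-imputation sentence are all those except the diagnosis. Each one measured after baseline also falls under the no-imputation sentence. Section 10.0 does not name TLFB; its inclusion follows from 2.4, 6.1 and 10.1.

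**Is there a hierarchical model for TLFB days?** Section 10.4.2 models the diagnosis only. Section 10.2 names descriptive, binomial and multinomial methods, with repeated-measures procedures for HIV risk only. Section 10.4 names mixed models for continuous and categorical measures, but only as something secondary analyses may use. So none is definitely specified.

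**Does any planned analysis vary the missing-data assumption?** Permutation tests do not. The comparison of the intent-to-treat and protocol populations changes who is analysed. The attrition analysis in 10.4.1 compares screen failures with randomized participants. The retention analyses describe dropout but do not re-estimate the treatment effect.

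**Amount of missing data (10.3).** 150 randomized, 50 per arm, 10-20% dropout. 150 × (1 − 0.20) = 120 reproduces the stated evaluable sample; at 10% it is 135. Per arm, 5 to 10 people would lack six-month data.

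**Size (a): the two rules in 10.0.** Assumptions not in the documents: normal outcomes with SD 1; interim-to-six-month correlation 0.4 or 0.6; dropout rising with interim use at a logit slope of 0.7 or 1.5 per SD; true effect 0.50 SD. With 50 per arm and 20,000 replicates, a t-test on observed cases was compared with a bivariate-normal maximum-likelihood model by arm, which stands in for multiple imputation.

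| Dropout, VI v DE | Observed-case estimate (rejects) | MAR likelihood estimate (rejects) |
|---|---|---|
| 10% v 15% | 0.47-0.49 (60-62%) | 0.50 (62-65%) |
| 10% v 20% | 0.44-0.48 (53-58%) | 0.50 (61-64%) |
| 15% v 15% | 0.50 (62-64%) | 0.50 (61-64%) |

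With no drug effect and unequal dropout, the observed-case estimate shifts by 0.01-0.06 SD against VI, and two-sided rejection is 5.1-6.2%.

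**Size (b): mean substitution, only if 10.4.1 were applied to an outcome.** Values missing completely at random, fraction m in each arm.

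- Arm mean: the reported standard error is about (1 − m) times the true one, so the type I error is about 2 × [1 − Φ(1.96 × (1 − m))]. At m = 0.10 this is 2 × [1 − Φ(1.764)] = 0.078; at m = 0.20 it is 2 × [1 − Φ(1.568)] = 0.117. Simulation with 50 per arm gave 0.079 and 0.116.
- Overall mean: the estimated difference is multiplied by (1 − m). 0.50 × 0.90 = 0.45 and 0.50 × 0.80 = 0.40, with type I error near 5%.

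**The case against.** The best defence is that the sections serve different purposes. The no-imputation sentence may describe likelihood estimation, the mixed models in 10.4 may be the models it refers to, and 10.4.1 may concern baseline variables, since it sits beside the balance checks. Each reading is possible. None is stated, 10.4 uses permissive wording, and the sentence in 10.4.1 has no limit. The contradiction within 10.0 remains.

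The size is also fairly challenged. The 0.44 end needs a 10% v 20% gap and the steeper slope. TLFB days are a 0-30 count, not normal. Some missed month-6 values could be recovered, because 8.2.1 collects use for each day since the last assessment and visits continue at months 7 and 12. Section 10.3 describes the trial as preliminary. These points limit the likely bias; they do not say which rule applies.

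Four stronger readings are tempting but not supported:

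- *The diagnosis rule contradicts the MAR sentence in 10.4.2.* The two can coexist: dropouts are assigned the diagnosis, and MAR would concern any other missing values.
- *Stopping medication might count as dropping out.* Section 7.3 speaks of ending participation. Section 7.13 lets people who opt out of medication continue assessments, so their diagnosis is observed.
- *Counting dropouts as diagnosed is an error favouring VI.* It shifts the arm difference by (1 − q) × the dropout gap, where q is the rate of opioid use disorder among dropouts. The documents do not give q. For assumed q of 0.5-0.9, a 5-point gap gives 0.5 × 5 = 2.5 down to 0.1 × 5 = 0.5 points, and nothing at q = 1. That supports a sensitivity analysis, not removal of the rule.
- *The ambiguity in 10.0 manufactures a benefit for VI.* Under the assumptions above, the observed-case bias runs against VI.

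**Conclusion.** The plan is wrong as written on this point and should be corrected. It states contradictory rules for the non-diagnosis outcomes, one of which is declared primary, and ranks neither these nor the additional rules in 7.3, 10.4 and 10.4.1. No named sensitivity analysis varies the missing-data assumption, although differential dropout is expected.

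The probable numerical effect is modest: up to about 0.06 SD on a 0.50 SD effect under the assumed unequal dropout, and none at equal dropout. It is larger only if mean substitution reaches an outcome, which 10.4.1 permits but may not intend. The textual finding does not depend on the simulations, which rest on normal data and assumed correlations and dropout slopes.

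**What to change.** 1. In 10.0, name one primary method for TLFB days and the other non-diagnosis outcomes: either multiple imputation by arm using baseline and interim TLFB and urine results, or a specified MAR likelihood model using those data. Delete the contradicting sentence, align 10.4, and state that the treatment-failure rule in 7.3 applies to the diagnosis only.
2. In 10.4.1, limit the missing-values sentence to baseline variables and covariates, and remove mean substitution and case elimination for outcomes.
3. Keep missing = diagnosis for people who end participation. State that those who stop medication but are assessed are analysed on their observed diagnosis. Give one explicit rule for any other missing six-month diagnosis: count it as a diagnosis, or multiply impute it. This is needed because 8.2.4 takes the diagnosis only at screening and six months. With one post-baseline value per person, the model in 10.4.2 would simply drop anyone without it, which is the case elimination that item 2 removes.
4. Add one multiple-imputation sensitivity analysis of the diagnosis under MAR, and report missing six-month diagnoses by arm.

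The cost is revised wording and a few more programmed analyses. No new data are needed, because TLFB is already collected at each visit in the medication phase (8.2.1). The sensitivity result may be less favourable than the main one.
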